10.1. Analysis of Primary Efficacy Endpoint

Phase 1b does not have a primary efficacy endpoint.

For Phase 2, the primary efficacy endpoint of ORR is defined as rate of CR + CRi+ CRp + MLFS + PR according to modified IWG AML response criteria as assessed by investigator. The analysis of the primary endpoint ORR will be based on the ITT population. Subjects will be analyzed as they were randomized, regardless of the actual treatment received. The ORR will be summarized by treatment arm. The treatment difference in ORR will be tested using the Chi-squared test or Fisher exact test if appropriate at a two-sided 0.2 level and in the ITT population. This test will provide the pivotal p-value for the comparison of the ORR of the oral AG-221 + SC azacitidine versus azacitidine mono therapy. Estimated response rate with 80% and 95% CIs will also be provided.

Response will also be summarized by the best overall response following the hierarchical order of CR, CRi/CRp, PR, MLFS, stable disease (SD), progressive disease (PD)/relapse, and not evaluable (NE). Cytogenetic Complete Remission (CRc) will be counted as CR thus will not be summarized separately. The best response of CRi and CRp are of the same rank and thus will be reported as a single category. The best response of PD, and relapse, will be grouped together. Sensitivity analyses will be performed on the mITT and EAP.

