10.2.3. Duration of Remission

Duration of remission is defined as time from first documented CR to documented morphologic relapse, PD, or death due to any cause, whichever occurs first. Subjects without morphologic relapse, PD, or death due to any cause will be censored at the date of the last response assessment.

The duration of remission will be analyzed using the KM method. The 25th percentile, median and 75th percentile time (including two-sided 95% CI) will be summarized for each treatment arm. Only subjects with documented CR as determined by investigator assessment will be included in the analysis.

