10.2.6. Complete Remission Rate

Complete remission rate is defined as rate of CR according to modified IWG AML response criteria.

Number and percentage of subjects with complete remission will be summarized by treatment arm. Comparisons between two treatment arms will be analyzed by Fisher's exact test if chi-square test is not appropriate.

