10.2.9. Time to Remission

Time to remission is defined as time from the first dose of study drug for Phase 1b subjects and the date of randomization for Phase 2 subjects to the first documented CR according to modified IWG AML response criteria.

Time to remission will be analyzed using the summary statistics for each treatment arm. Only subjects with documented CR as determined by investigator assessment will be included in the analysis.

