17.4. International Working Group Acute Myeloid Leukemia Response Criteria

Hematologic Response According to modified IWG Criteria for AML	
Category	Definition
Morphologic Complete Remission (CR)	Defined as less than 5% blasts in a BM aspirate sample with marrow spicules and with a count of at least 200 nucleated cells. There should be no blasts with Auer rods and absence of extramedullary disease. Plus, all the following conditions should be met: 
 ANC $\geq 1 \times 10^9/L$ (1,000/μL) Platelet count $\geq 100 \times 10^9/L$ (100,000/μL) Independent of red cell transfusions for ≥ 1 week immediately before each response assessment
Morphologic Complete Remission with Incomplete Neutrophil Recovery (CRi)^a	Defined as all criteria of morphologic CR except the following: 
 ANC $< 1 \times 10^9/L$ (1,000/μL)
Morphologic Complete Remission with Incomplete Platelet Recovery (CRp)^a	Defined as all criteria of morphologic CR except the following: 
 Platelet count $< 100 \times 10^9/L$ (100,000/μL)
Morphologic Leukemia-free State (MLFS)	Defined as less than 5% blasts in a BM aspirate sample with marrow spicules and with a count of at least 200 nucleated cells. There should be no blasts with Auer rods and absence of extramedullary disease
Partial Remission (PR)	Defined as all hematologic criteria of morphologic CR with a $> 50\%$ decrease in the percentage of BM blasts to 5% to 25% (a blast count value of $< 5\%$ may also be considered a partial remission if Auer rods are present) ^b
Cytogenetic Complete Remission (CRc)	Defined as CR/CRi/CRp with a reversion to a normal karyotype in cases with an abnormal karyotype at baseline, based on evaluating ≥ 20 metaphase cells from BM
Morphologic Relapse after CR/CRi/CRp^a	Defined as one of the following conditions: 
 Reappearance of $\geq 5\%$ blasts in the BM not attributable to any other cause (eg, BM regeneration after consolidation therapy); or Development of extramedullary disease
Not evaluable (NE)^a	Defined as without a post-treatment response assessment
Stable Disease (SD)^a	Defined as failure to meet any of the above criteria and not meeting the criteria of progressive disease (see below)

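### SAP 10.1 counts every cytogenetic complete remission as CR although CRc includes CRi and CRp, so the best-response table can misclassify subjects and the rule conflicts with the CR rate in 10.2.6

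*SAP*

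**What the plan says.** SAP 10.1 defines the primary endpoint, ORR, and then adds a descriptive table: "Response will also be summarized by the best overall response following the hierarchical order of CR, CRi/CRp, PR, MLFS", continuing down to stable disease, progression or relapse, and not evaluable. Two classification rules follow. One is that "Cytogenetic Complete Remission (CRc) will be counted as CR thus will not be summarized separately". The other is that "The best response of CRi and CRp are of the same rank and thus will be reported as a single category".

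SAP 17.4 and Protocol Appendix F give the same definition of CRc: "Defined as CR/CRi/CRp with a reversion to a normal karyotype in cases with an abnormal karyotype at baseline", based on at least 20 metaphases. In the same tables CR requires ANC of at least 1 x 10^9/L and platelets of at least 100 x 10^9/L. CRi and CRp are each "Defined as all criteria of morphologic CR except the following": ANC below 1 x 10^9/L for CRi, platelets below 100 x 10^9/L for CRp.

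Three later sections rest on CR. In 10.2.6, "Complete remission rate is defined as rate of CR according to modified IWG AML response criteria". In 10.2.3, "Duration of remission is defined as time from first documented CR to documented morphologic relapse, PD, or death due to any cause". For time to remission, 10.2.9 says "Only subjects with documented CR as determined by investigator assessment will be included in the analysis". None of the three mentions CRc.

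**The concern.** CRc describes the karyotype and can accompany any of three morphologic responses. The 10.1 rule treats it as a form of CR, with no restriction to CRc that arises from morphologic CR. A subject who by definition lacks neutrophil or platelet recovery can therefore appear in the CR row.

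The output directly exposed is the best overall response table. SAP 8.5 also breaks transfusion independence down by best response, with CR and CRi/CRp as separate categories, so that summary inherits the classification.

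Beyond that table, the SAP contains no other instruction on CRc. A programmer deriving the complete remission rate could apply the 10.1 rule, or could apply the modified IWG criteria named in 10.2.6. The same data would then give two different CR rates. The complete remission rate is a listed Phase 2 secondary endpoint compared between arms, so it should have one derivation.

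**Working it through.** **1. The plan's own figure, to show what is not at stake.** The only design figure nearby is the 75% power for ORR in SAP 4.4 and Protocol 9.3: 50% versus 30%, 66 versus 33 subjects, two-sided alpha 0.2.
- Pooled rate: (66 x 0.50 + 33 x 0.30)/99 = 0.4333.
- Null SE: sqrt(0.4333 x 0.5667 x (1/66 + 1/33)) = 0.1056.
- Alternative SE: sqrt(0.30 x 0.70/33 + 0.50 x 0.50/66) = 0.1008.
- Power: Phi((0.20 - 1.2816 x 0.1056)/0.1008) = 73.9%. Exact enumeration of the uncorrected chi-square gives 75.3%.

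The stated figure reproduces. It does not depend on the CRc rule, because CR, CRi and CRp all count as responses in ORR.

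**2. One hypothetical subject under each section.** Take under 5% blasts with every CR criterion met except platelets, which are 40 x 10^9/L, and an abnormal baseline karyotype that has reverted.

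| Source | Classification |
|---|---|
| SAP 17.4 and Protocol Appendix F, morphologic | CRp |
| SAP 17.4 and Protocol Appendix F, cytogenetic | CRc (arising from CRp) |
| SAP 10.1, CRi/CRp category | CRi/CRp |
| SAP 10.1, CRc rule | CR |
| SAP 10.2.6, modified IWG CR | Not CR |

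**3. Can the case arise?** Protocol 6.2 and 6.5.1 call for a cytogenetic preparation when an aspirate is taken to confirm CR, CRi or CRp, so it can. Footnote cc of Protocol Table 4 is narrower and names only CR, relapse and progression.

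**4. Effect per subject, if the rule is carried into the CR rate.** 1/66 = 1.5 points; 1/33 = 3.0 points.

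**5. Possible size within an arm (assumed inputs).** Overstatement = i x k x r, where i is the share of the arm with best response CRi/CRp, k the share of those with an abnormal baseline karyotype, and r the share of those reverting. The documents give none of these. Assume i = 5-20%, k = 30-50%, r = 25-75%.
- Low: 0.05 x 0.30 x 0.25 = 0.4 points, or about 0.2 of 66 subjects and 0.1 of 33.
- High: 0.20 x 0.50 x 0.75 = 7.5 points, or about 5 of 66 subjects and 2.5 of 33.

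**6. Possible size between arms (assumed inputs).** Suppose 10 CRi/CRp in the combination arm and 3 in the control arm, with k = 40% and r = 25-75% in both.
- Combination: 10 x 0.4 x (0.25 to 0.75) = 1 to 3 subjects, or 1.5 to 4.5 points.
- Control: 3 x 0.4 x (0.25 to 0.75) = 0.3 to 0.9 subjects, or 0.9 to 2.7 points.
- Net: 1.5 - 0.9 = 0.6 points, to 4.5 - 2.7 = 1.8 points.

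If i, k and r were equal in the two arms, the expected net effect would be zero.

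**7. Time-based outputs, if carried over.** A subject with CRc on a CRp marrow who later reaches morphologic CR gets an earlier remission date, so time to remission shortens and duration of remission lengthens. A subject who never reaches morphologic CR is added to both analyses.

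**The case against.** The strongest reply is that the CRc sentence belongs to a descriptive table, while the complete remission rate has its own definition. Read alone, 10.2.6 excludes these subjects, because the modified IWG criteria require both counts. This stands in part. A reader might infer from 10.1 that subjects without count recovery do enter the complete remission rate, but the SAP never says so. Carry-over is the natural reading only because 10.1 holds the sole CRc instruction. What the documents establish is a misclassification in the best-response table and a conflict with 10.2.6.

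Second, the rule bites only if CRc is recorded in place of CRi or CRp. If the eCRF keeps morphologic response and cytogenetics apart, a CRp subject may stay CRp. The documents do not show the form, so this remains open. It does not make the written rule correct.

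Third, sponsor-derived CR (10.2.10) and CR plus CRh (10.2.11) come from laboratory data and would expose an inflated investigator rate. They are a useful partial check, but they do not correct the investigator endpoint.

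Fourth, it may be said that only CRc with full morphologic CR was meant. The text does not say that; if it was the intention, the change merely records it.

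**Conclusion.** Wrong as written, of moderate severity. That SAP 10.1 assigns to CR some subjects whom SAP 17.4 and Protocol Appendix F place in CRi or CRp follows from the text alone and needs no assumption. The effect on the CR rate, duration of remission and time to remission is conditional on the rule being carried over.

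The size per subject is fixed at 1.5 or 3.0 points by arm. The number of subjects is unknown, and the ranges in steps 5 and 6 rest wholly on assumed inputs.

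A reader might go further and conclude that the rule favours AG-221. The documents do not support a direction: the net effect depends on the proportion of CRi/CRp, the baseline karyotype and the reversion rate in each arm, and the assumed illustration nets to only 0.6 to 1.8 points. Nor does the problem reach the primary analysis. ORR, duration of response, time to response, EFS and OS do not depend on the split between CR and CRi/CRp. Time to remission is descriptive, and neither it nor duration of remission appears in the endpoint tables of either document. The listed endpoint at risk is therefore one secondary rate, which is why this falls short of a must-fix.

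**What to change.** Replace the CRc sentence in SAP 10.1 with: *CRc is a cytogenetic qualifier; a subject with CRc is classified by the investigator's underlying morphologic response (CR, CRi or CRp), and only CRc with morphologic CR counts as CR.* Cross-reference it in 10.2.3, 10.2.6 and 10.2.9.

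The investigator's category should be kept, not re-derived from laboratory counts. Re-derivation would override an investigator-assessed endpoint and partly duplicate sponsor-derived CR.

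The cost is one sentence and one derivation rule, and the reported CR rate may be slightly lower. The protocol's amendment justification says the primary analysis report was already final by 15 Dec 2020, so acting on this may mean re-deriving and footnoting the CR outputs.

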10.2. Analyses of Secondary Efficacy Endpoints

For Phase 1b, ORR and Sponsor Derived CR/CRh (based on laboratory dataset) are secondary efficacy endpoints and will be analyzed based on the FAP population and on the EAP as sensitivity analysis. These endpoints will be presented descriptively with 95% and 90% CI. Other measures of clinical activity, including duration of response, duration of CR/CRh, duration of remission, time to response, time to remission, time to CR/CRh, event-free survival (EFS), and overall survival may be summarized as appropriate in the FAP population.

For Phase 2, time-to-event secondary efficacy variables are displayed as part of [Table 2](#) (EFS, duration of response, OS, duration of remission (CR), and duration of sponsor assessed CR and CRh) will be analyzed by the KM method if appropriate to estimate time-to-event curves. In addition, Cox proportional hazards regression models will be generated to obtain hazard ratios and their two-sided 95% CI, and the p-value will be based on 2-sided log-rank test as appropriate. Time to response, time to remission, and time to sponsored assessed CR and CRh will be summarized

descriptively. Counts and percentages will be used to describe categorical variables. Rates, such as Complete remission rate, Hematologic improvement rate, sponsor derived CR and CR + CRh, will be analyzed similarly to ORR. All secondary efficacy endpoints for Phase 2 will be analyzed based on ITT population and on the mITT as supportive evidence and to assess the robustness of the efficacy findings. Subjects will be analyzed according to randomized treatment arm.

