10.2.2. Duration of Response

Duration of response is defined as time from first documented CR/CRi/CRp/PR/MLFS to documented morphologic relapse, PD, or death due to any cause, whichever occurs first. Subjects without morphologic relapse, PD, or death due to any cause will be censored at the date of the last response assessment.

The duration of response will be analyzed using the KM method. The 25th percentile, median and 75th percentile time (including two-sided 95% CI) will be summarized for each treatment arm. Only subjects with documented CR/CRi/CRp/PR/MLFS response as determined by investigator assessment will be included in the analysis.

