10.2.12. Duration of Sponsor Assessed CR and CRh

Duration of sponsor assessed CR and CRh is defined as time from first documented CR/CRh to documented morphologic relapse, PD, or death due to any cause, whichever occurs first. Subjects without morphologic relapse, PD, or death due to any cause will be censored at the date of the last response assessment.

The duration of response will be analyzed using the KM method. The 25th percentile, median and 75th percentile time (including two-sided 95% CI) will be summarized for each treatment arm. Only subjects with documented CR/CRh response as determined by sponsor assessment will be included in the analysis.

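### SAP 10.2 attaches Cox hazard ratios, and a discretionary log-rank p-value, to three responders-only duration endpoints, where the arm comparison is not randomised

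*SAP*

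**What the plan says.** SAP 10.2 sets one rule for the Phase 2 time-to-event secondary endpoints. Its list reads "EFS, duration of response, OS, duration of remission (CR), and duration of sponsor assessed CR and CRh) will be analyzed by the KM method", with a qualifier that this applies if appropriate. The next sentence adds that "Cox proportional hazards regression models will be generated to obtain hazard ratios and their two-sided 95% CI" and that "the p-value will be based on 2-sided log-rank test as appropriate". No endpoint in the list is exempted. The same section then states that "All secondary efficacy endpoints for Phase 2 will be analyzed based on ITT population and on the mITT as supportive evidence".

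The endpoint sections restrict who enters the three duration analyses:

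- SAP 10.2.2, duration of response: "Only subjects with documented CR/CRi/CRp/PR/MLFS response as determined by investigator assessment will be included in the analysis".
- SAP 10.2.3, duration of remission: "Only subjects with documented CR as determined by investigator assessment will be included in the analysis".
- SAP 10.2.12, duration of CR/CRh: "Only subjects with documented CR/CRh response as determined by sponsor assessment will be included in the analysis".

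The clock starts at response, not at randomisation: "Duration of response is defined as time from first documented CR/CRi/CRp/PR/MLFS to documented morphologic relapse, PD, or death due to any cause". For method, each of these sections names Kaplan-Meier quartiles with 95% CIs per arm. None names a hazard ratio or a test. Protocol 9.6.2 likewise gives duration of response Kaplan-Meier estimates and CIs only, while naming log-rank and Cox for EFS and log-rank for OS.

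**The concern.** Response is an outcome of treatment. In Phase 2 it is the primary outcome, and the design expects the combination to produce more of it. The combination responders will then include patients who would not have responded to azacitidine alone, and the control responders have no matching group. Randomisation balances the arms as randomised; it does not balance these two subsets. A hazard ratio between them mixes any drug effect on duration with the difference in who responded. EFS and OS start at randomisation, include everyone, and do not have this problem.

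The risk is that a reader of the results takes a duration hazard ratio, printed beside those for EFS and OS, as a treatment effect of the same standing. Nothing in the SAP labels it descriptive or warns that it is conditional on response.

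**Working it through.** **1. Inputs from the documents (SAP 4.4).** 66 v 33 subjects; planning ORR 50% v 30%; two-sided alpha 0.2; stated power 75%. SAP 10 sets alpha 0.05 for tests not otherwise specified.

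**2. The plan's own figure.** Pooled ORR = (33 + 9.9)/99 = 0.433. Standard error under the null = √(0.433 × 0.567 × (1/33 + 1/66)) = 0.1056; under the alternative = √(0.21/33 + 0.25/66) = 0.1008. Power = Φ((0.20 − 1.282 × 0.1056)/0.1008) = 73.9%. Exact enumeration of the uncorrected chi-square test gives 75.3%. The stated 75% reproduces. The documents give no figure for any duration endpoint.

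**3. Who is compared.** Expected responders: 66 × 0.50 = 33 and 33 × 0.30 = 9.9, so about 43 of 99 randomised. The 95% binomial range for the control count is 5 to 15. Investigator CR is one component of ORR, so the duration-of-remission set is no larger. No planning rate is given for CR/CRh.

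**4. Size of the selection effect.** All durations here are assumptions. The 30% who would respond on either arm have median duration 18 months on both arms, so the drug does not change their duration. A further 20% respond only on the combination, with median m. They make up 20/50 = 40% of combination responders. Durations are exponential and censoring is uniform at 12 to 30 months.

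The hazard ratio at time zero is 0.6 + 0.4 × 18/m. It then drifts as the mix of remaining responders changes, and Cox averages over follow-up. Large-sample Cox values by simulation:

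| m (months) | HR at time 0 | Cox HR, large sample |
|---|---|---|
| 6 | 1.80 | 1.52 |
| 9 | 1.40 | 1.32 |
| 12 | 1.20 | 1.18 |
| 18 | 1.00 | 1.00 |
| 27 | 0.87 | 0.86 |

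With a common median of 12 months instead of 18, and m from 4 to 18 months, the range is 1.47 to 0.85.

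**5. Precision in the planned sample.** SE(log HR) = √(1/events₁ + 1/events₂). Assuming 60% of responders have an event: √(1/19.8 + 1/5.94) = 0.468, and exp(±1.96 × 0.468) gives a 95% CI factor of 0.40 to 2.50. If all 43 responders have an event, the factor is 0.49 to 2.03; with only 20 events it is 0.35 to 2.83.

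In simulated trials with 33 v 10 responders and m = 9, the estimate exceeds 1 in about 70% of trials. The log-rank test at 0.05 rejects in about 7%. Across m = 6 to 27 it rejects in about 5% to 12%, highest at m = 6.

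**6. Ability to detect a real effect.** By Schoenfeld's formula, power = Φ(|ln HR| × √(D × 0.769 × 0.231) − 1.96). For HR 0.6 and D = 20 to 43 events, power is 16% to 29%. Power of 80% needs an HR of about 0.23 to 0.36.

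**7. Consistency.** SAP 10.2 places all secondary endpoints on the ITT population; 10.2.2, 10.2.3 and 10.2.12 admit responders only. Both cannot hold. SAP 10.2 already limits time to response, which is also responders-only, to descriptive summary.

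**The case against.** The strongest reply is that the specific sections already do the right thing. SAP 10.2.2, 10.2.3 and 10.2.12 give Kaplan-Meier quartiles per arm and no test. Where the SAP wants an arm comparison it says so: 10.2.1 names log-rank and Cox for EFS, and 10.2.4 treats OS the same way. Cox on durations rests on one umbrella sentence. This stands in part: the defect is as much an internal inconsistency as a settled choice. But the umbrella sentence presents Cox as an addition to Kaplan-Meier, and the endpoint sections do not exclude it, so a programmer following 10.2 would produce the hazard ratios.

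Second, a reader might infer that the SAP commits to log-rank p-values for durations. The text does not support that. The hedge on the log-rank test makes the p-value discretionary, though no criterion is stated; only the Cox hazard ratio is unhedged.

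Third, a reader might infer that the hazard ratio will point to harm from AG-221. That does not follow. The documents give no durations. The direction depends on whether the extra responses are shorter or longer than the common ones, and with about 10 control responders chance dominates.

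Fourth, the consequence is limited. These are secondary endpoints, the pivotal p-value is for ORR in the ITT population, and EFS and OS give all-randomised comparisons beside them. This stands and limits the severity.

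**Conclusion.** The point holds in a limited form. As written, SAP 10.2 calls for hazard ratios on three endpoints whose analysis sets are selected after randomisation by an outcome planned to differ between arms. It exceeds the SAP's own endpoint sections and, for duration of response, protocol 9.6.2. (Protocol 9.6.2 leaves the method for duration of CR/CRh open, so no conflict with the protocol is claimed there.) It also contradicts the SAP's ITT statement.

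Under the assumed scenarios the large-sample hazard ratio lies between about 1.5 and about 0.85 with no drug effect on duration in common responders. The planned sample gives a 95% CI factor of about 0.4 to 2.5. The estimate can mislead either way; a falsely significant result would be uncommon, at or modestly above the nominal 5%. These sizes rest on assumed medians, censoring and event share; only the responder counts come from the plan. It would be wrong to conclude that the trial's efficacy findings are compromised: primary ORR, EFS and OS use all randomised subjects and are unaffected. Severity is low to moderate.

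**What to change.** In SAP 10.2, limit the Cox and log-rank sentence to EFS and OS. Report duration of response, duration of remission and duration of CR/CRh as per-arm Kaplan-Meier quartiles with CIs, labelled descriptive and responders-only, without hazard ratio or p-value. Amend the ITT sentence to except these endpoints.

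If a comparison of durability is wanted, use a measure defined for all randomised subjects, such as the probability of being in response over time, with non-responders counted as never in response.

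The cost is SAP wording and fewer outputs; the restriction needs no new data. The protocol's latest amendment justification reports that the primary-analysis study report is already final. The change would therefore govern later analyses, and any duration hazard ratio already produced should carry the descriptive, responders-only label. The documents do not show whether one was produced.
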